This study will include a vulnerable population: children.

- 1) Age inclusive of and between 6 and 12 years at the time of enrollment; 2) Verbally willing to agree to swallowing a maximum of 9-12 capsules/day with food, attend all study appointments and complete questionnaires; and 3) Meet criteria for ADHD as assessed by the clinical cut-off (6+ questions scored as 2s or 3s, “often,” or “very often,” or sufficient “sometimes” responses to meet a score of 6) on the Category A: ADHD questions from on the Child & Adolescent Symptom Inventory-5 (CASI-5) with at least several symptoms present in more than 1 setting, based on the DSM-5 symptom criteria, including significant impairment in functioning socially and/or academically⁴¹; 4) Demonstrate at least one symptom of irritability or anger as assessed by a score of 2 or 3 from an “often,” or “very often” response on one question from Category B or Rz from the CASI-5; or two “sometimes” responses; 5) Be medication-free, or washout with medical supervision to be provided by the child’s pediatrician or primary care physician, reliant on the parent/guardian to work with that physician, for *at least 2 weeks* prior to in-person study assessment. 5) Willing to give blood sample at two time points: baseline, week 8; week 16 is optional.

Participants identified as having trouble swallowing pills during the phone will be asked to complete the pill swallowing program developed by Kaplan et al[48] and successfully complete this prior to being invited to come in for a lab visit. The video can be viewed at:

Child RCT Protocol 2017

<http://research4kids.ucalgary.ca/pillswallowing>. Children who continue to be unable to swallow the pills after completing the pill swallowing program will not be included in the study.

Exclusion criteria

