- 1) Neurological disorder involving brain or other central function (e.g., history of or suspected intellectual disability, autism spectrum disorder, epilepsy, multiple sclerosis, narcolepsy) or other major psychiatric condition requiring hospitalization (e.g. significant mood disorder, active suicidal ideation, or psychosis), based on parent/guardian self-report of child's condition and response to category M on the CASI-5 subscale; 2) Any serious medical condition, including inflammatory bowel disease, history of cancer, kidney or liver disease, hyperthyroidism, diabetes Type I or II; 3) Known allergy to any ingredients of the intervention; 4) Any known abnormality of mineral metabolism (e.g., Wilson's disease, hemochromatosis); 5) Taking any other medication with primarily central nervous system activity, including stimulants, within the last 2 weeks prior to in-person assessment; participants must be off these medications for a minimum of two weeks prior to the screening 6) Severe separation anxiety that would preclude separating from parent/guardian to answer study questionnaires; 7) Any disability that would interfere with participant answering questions verbally; 8) Non-English speaking; 9) Pregnancy or sexually active at baseline. Exclusion criteria 1-6 and 9, will be based on parent/guardian self-report of child's condition. If the parent/guardian reports medical exclusion criteria, or concerns about eligibility, data provided by parent/guardian will be confirmed by review of medical records with release of information signed by parent/guardian. Potential participant may be reviewed in-person by study physician in the case of any concerns about participation.

The data collected from potential participants who are not included in the study due to screening failure will be securely stored (as outlined below) until the end of the study for the purpose of including in the recruitment section of the CONSORT diagram.

Setting and Recruitment methods

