Each site will submit an identical protocol to their internal IRB or ethics committee. All study protocols and materials (identical for each site, except where differentiation or specification is required by an individual IRB) will be approved by the IRB/ethics committee at that site. Details concerning coordination of activities are located in the Multi-Site Coordination section.

Phone screen

At initial phone contact, which will be initiated following contact from the potential participants, a study coordinator/research associate will conduct a phone screen with interested families by outlining the purpose of the study, confirming willingness to participate by asking eligibility questions from the inclusion and exclusion criteria below. Parent/guardians of females will be asked if they have begun menstruating. If yes, parent/guardian will be asked whether child is sexually active. If yes, or unsure, potential participant will need to take a urine test at baseline as a pregnancy screen. Any questions of the parent/guardian and potential participant will be answered as well. Parent will be asked for the email address of a teacher, coach, or other adult who knows the child, and CASI-5 questions will be sent to that person to answer on behalf of the child. The questionnaire will be sent to the teacher or named adult using the email provided, via the secure REDCap system.

Child RCT Protocol 2017

Only children who are ADHD-medication-free for at least 2 weeks prior to in-person assessment will be scheduled for an in-person screening assessment and considered for participation. A phone screen process has been used with success in multiple previous studies by one of the co-investigators [49] If the child is eligible based on the screening, the parent will be send the CASI-5 screening questions to their email via REDCap. The screening questions come from the ADHD and DMDD/ODD sections of the CASI-5 (see details of this process in the Baseline Assessment section below).

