Phone screen data, including inclusion/exclusion criteria, and the CASI-5 responses will be reviewed and discussed by the study PIs and the research assistant. Any questions or concerns regarding enrollment, based on information provided by the parent/guardian or participant, may be handled with phone or in-person consultation with an onsite study physician. If necessary, the consultation or meeting enables a brief review of medical history and the opportunity to identify any potential concerns prior to enrollment.

Consent and Assent

After eligibility is established based on phone screen and CASI-5 responses, and review of medical records and/or site physician assessment, if necessary, the parent/guardian and child will be invited to meet with a research staff team member for a baseline visit, in designated office space at one of the three sites to discuss the study and to complete consent and assent prior to any study procedures. Prior to the first visit, the consent and assent forms will be sent to the parent/guardian for review in before the first meeting. This will facilitate the parent's ability to formulate and ask questions in advance of the first visit. The consent will be signed onsite, using REDCap.

As this study represents minimal risk to the child and offers potential benefit, the consent of one parent/guardian will be sufficient for participation. The child will be provided with information about the study using simple language that is appropriate for a child as young as 6 years of age. The child will be clearly told that s/he does not have to participate, s/he can change his/her mind at a later time. Provided that both the parent/guardian and child want to participate, both will provide electronic consent/assent via the secure, HIPAA-compliant REDCap web portal. Documentation of assent/consent, via an electronic signature, will be captured for each participant and parent/guardian. If the parent/guardian or child does not consent/assent or is excluded for any other reason, data already collected will be retained for the purpose of characterizing those who made contact. The reason for not enrolling will be noted in REDCap. Parents will be asked whether they are interested in communicating regarding the MADDY research study via text. A separate consent form will be provided and the text communication explained.

Procedures

Baseline Assessment

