Once parent/guardian has signed consent and child participant has signed assent, and following the completion of baseline questionnaires and recording of vitals, including blood pressure, pulse, height and weight, the participant will be considered to be enrolled in the study. Enrollment may be delayed until any questions that may have arisen during the baseline assessment are discussed with and answered by the study physician. Once enrolled, the participant will be randomized to a treatment, either active or placebo, and a notification of participation letter will be sent to the child's primary care physician with the parent/guardian signature on the release of information form. Parent/guardian will be given study capsules for the initial 4 weeks as noted below.

Randomization

The randomization scheme will be generated for all three sites, as a whole, by the study statistician at OHSU using REDCap, with the randomization sequence arranged in permuted blocks of size 5, in a 3 active to 2 placebo ratio. The randomization scheme will be emailed to the other two sites. Neither the participants nor the clinicians involved in the study will have access to the randomization until end of study, but access will be available to the medical oversight person at each site and Data Safety Monitoring Board members in event of emergency. A pharmacist or designated unblinded research team member at each site will prepare individual participant pill kits in advance, per the randomization scheme. The pill kits include 1-week pill caddy containing the capsules to be taken during the first week (titrated up to the full dose by Day 5), from pre-labeled and packaged bottles sent from the manufacturer. The pill caddy, together with the bottle of pills for the rest of the month will be individually labeled and put inside a white paper bag to be given to each participant. These kits will be sequentially numbered and allocated to placebo or micronutrients based on the randomization list. The pharmacy research staff at OHSU, who is unblinded, will be available 24/7

Child RCT Protocol 2017

as per on-call schedule, to break the blind for an individual subject if medically necessary. Each participating family will be given the appropriate local clinician name and contact information in the case of a side effect or question or urgent notification for any medical emergencies.

Micronutrient formula, titration and dosing

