One risk for participants, if they were taking stimulant medication that conferred a benefit in terms of ADHD symptoms, is that by coming off the medication, their symptoms may return. Risks to participants in terms of taking the micronutrients are low, but as with any intervention there are potential side effects. These may include transient gastrointestinal upset (loose stool, nausea), and headache, particularly if product is taken on an empty stomach. If these side effects are experienced and believe to be related to taking the micronutrients, these symptoms should go away if pills are taken with food and water as directed, and tend to lessen after a day or two of taking the pills, or when participant ceases taking the pills. Not all participants will receive the active treatment in the first 8-weeks, but everyone will have the opportunity to knowingly take the active treatment in the second 8-week, open-label phase. In terms of specific personal benefit, some participants may find that taking the micronutrients help with the symptoms of ADHD and irritability, as well as aggressive behavior. However, participants may or may not personally benefit from being in this study.

The product to be studied has the largest amount of published research in the mental health field for a complex micronutrient product. Data were examined from all known published and unpublished

Child RCT Protocol 2017

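### A child who stops ADHD medication in order to qualify starts the washout at least 14 days before consent is first signed, with no study safety contact scheduled in between

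*Combined protocol and SAP*

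**What the plan says.** - **Eligibility.** The Inclusion Criteria offer two routes on medication: "Be medication-free, or washout with medical supervision to be provided by the" child's pediatrician or primary care physician, for at least 2 weeks before the in-person assessment. Arranging this is "reliant on the parent/guardian to work with that physician".
- **Scheduling.** The Phone screen section makes the medication-free period a condition of getting a visit: "Only children who are ADHD-medication-free for at least 2 weeks prior to in-person assessment will be scheduled for an in-person screening assessment".
- **Exclusion.** The same two weeks are counted in one sentence from the in-person assessment and also from another term: "participants must be off these medications for a minimum of two weeks prior to the screening".
- **Consent.** After eligibility is established, the family is invited to the baseline visit "to discuss the study and to complete consent and assent prior to any study procedures". The forms go to the parent for review before that visit, but "The consent will be signed onsite, using REDCap". Table 1 marks Consent and Assent in the baseline column only.
- **Risk.** The Risk/benefit analysis opens with the child who was benefiting from stimulant medication. The risk "is that by coming off the medication, their symptoms may return".
- **Physician.** Under Enrollment, once the child is enrolled, "a notification of participation letter will be sent to the" child's primary care physician.
- **Recording.** Table 1 starts adverse events, PAERS, CSSRS and concomitant treatment at baseline. Its phone-screen column holds only the screen itself with the CASI-5 eligibility questions.

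**The concern.** The trial sets the medication-free condition and counts the return of symptoms as one of its own risks. For a child who stops treatment to meet that condition, exposure to the risk begins before the parent has consented or the child has assented. The child is told that taking part is optional at a visit held after the washout is complete. The Consent and Assent section itself foresees families who decline or are excluded at that stage, so some children could go through a washout for a trial they never enter.

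The safety account is also affected. A child who gets worse during the washout and does not attend leaves no scheduled adverse-event record, only a contact with a reason for not enrolling. The first participant risk that the protocol names is thus one that its schedule is not set up to observe.

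**Working it through.** The plan gives no figure to reproduce. The check is one of order. Take the baseline visit as day 0.

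| Step | Timing | Source |
|---|---|---|
| Phone screen and CASI-5 eligibility questions | before day 0 | Phone screen; Table 1 |
| Medication stopped by a child who needs a washout | day −14 or earlier (2 weeks × 7 = 14 days) | Inclusion Criteria; Phone screen |
| Forms sent to the parent to read | before day 0, no lead time stated | Consent and Assent |
| Consent and assent signed | day 0 | Consent and Assent; Table 1 |
| First PAERS, CSSRS and concomitant-treatment record | day 0 | Table 1 |
| Letter to the child's physician | after enrollment, so day 0 or later | Enrollment |

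1. Gap from start of washout to signature: 0 − (−14) = 14 days at least.
2. Gap from start of washout to first scheduled safety record: the same, at least 14 days.
3. Gap from start of washout to the study letter: at least 14 days, because enrollment comes after consent, baseline questionnaires and vital signs.
4. What the baseline record could recover: the concomitant treatment measure (Parent/guardian-rated measures) asks for start and stop dates, but about current treatments. A drug already stopped may or may not be entered. PAERS is given at baseline, but the documents do not say whether its recall period reaches back over the washout. Neither reaches a child who does not attend.
5. Who is affected: a child must be on a medication that has to be stopped at first contact, and must stop it in order to take part. Children already medication-free have no study-driven washout. The documents do not give the share in either group.
6. Terms for the reference visit: the Inclusion Criteria use the in-person study assessment. The Exclusion criteria use both the in-person assessment and the screening. The Phone screen section uses both the in-person assessment and an in-person screening assessment, while the Design Overview says that participants are screened by phone.

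**The case against.** The strongest reply is that the washout is medical care outside the trial. The child's own physician supervises it, the parent has the forms before the visit, eligibility is settled by phone screen and CASI-5 before the invitation, and a study physician can be consulted before enrollment if concerns arise. These safeguards are real, and they rule out several stronger readings that a reader might draw.

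- *The washout is unmonitored.* It is not: the Inclusion Criteria require medical supervision. What is absent is scheduled monitoring by the study.
- *The washout is unrecorded.* That goes too far. The baseline measure asks for stop dates, and reasons for not enrolling are kept. What is absent is an explicit washout record.
- *The physician knows nothing of the study.* The documents do not say so. The parent works with the physician and may pass on the forms. The documents show only that the one study letter they describe comes after enrollment.
- *Children spend 14 + 56 = 70 days off treatment without consent.* The 56 blinded days come after consent and do not belong in this count.
- *A definite number of children is affected.* Any count needs an assumed share. Taking 20% to 50% of 135 would give 27 to 68, but nothing in the documents supports either end.
- *The Exclusion criteria push the stop back before the phone call.* The screening there can equally mean the in-person screening assessment named in the Phone screen section. The terms need reconciling, but an earlier stop is not shown.

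One caution also stands. Part of the text under Setting and Recruitment methods was not available for this review, so earlier counseling or contact described there cannot be excluded.

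The order itself survives the reply. Receiving a form is not consent, and its dispatch is not tied to the start of the washout. The explicit on-site signing rule and Table 1 place signature at baseline.

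**Conclusion.** The point holds for a defined group: children on ADHD medication at first contact who stop it in order to qualify. For them the plan as written puts a risk that it names itself at least 14 days before signed consent and assent. Supervision is left to the child's own physician, and no study safety contact, adverse-event capture or explicit washout record is scheduled before baseline. This sits badly with the plan's own undertaking that consent precedes study procedures.

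The 14 days is a minimum that follows directly from the text. The size of the group is unknown. The conclusion assumes that the on-site signing rule and Table 1 govern, and that no unavailable text sets an earlier consent step for these children. It concerns consent and safety recording. It does not touch the randomized comparison or the sample size, and it takes no position on whether or how long medication should be stopped. It is best treated as a cheap improvement.

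**What to change.** - For any child who would stop medication in order to take part, obtain parent consent and child assent before the washout begins. The advance forms and REDCap electronic signature already exist; what changes is the timing and, for this group, the on-site signing rule.
- Send the physician letter at that point, with the parent's signed release.
- Record the washout start and stop dates and any events during it, at the latest by asking about them explicitly at baseline. State how events are recorded for a child who consents but does not attend.
- Keep on-site consent for children who are already medication-free.
- Use one term for the reference visit in the Inclusion Criteria, Exclusion criteria and Phone screen sections.

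No washout length or other clinical rule is proposed.

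The cost is an amendment to the consent section and Table 1, approved by the IRB or ethics committee at each of the three sites. If washout events are to be recorded as adverse events, the wording of the adverse-event definition, which refers to events in the course of the trial, should be checked. Some families will consent and then not be randomized, which adds a few post-consent screen failures to the CONSORT diagram.

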The design is an 8-week randomized, double-blind, placebo-controlled trial, with an 8-week open-label extension, of Daily Essential Nutrients (DEN; Hardy Nutritionals), and a 30-, 60-, and 365-day follow-up phone call or in person-visit. The follow-up calls will also assess for safety following study completion. Parent/guardian and child ratings, using standardized measures, will evaluate adherence, side effects and AEs (Aim 1); ADHD-associated mood and irritability (Aim 2); and ADHD symptoms (Aim 3), thus allowing evaluation for clinical significance. Other domains of psychopathology will be evaluated for purposes of sample characterization and secondary analyses. The design consists of three study periods, which are individualized for each participant as they enroll:

Child RCT Protocol 2017

1. Screening and baseline. Participants will be screened by phone through a conversation with the parent/guardian for study eligibility. Those who are eligible and consent/assent to the study will receive a baseline assessment (see below for definition of eligibility and assessment).
2. An 8-week period of fully randomized, placebo-controlled, treatment.
3. An 8-week open-label extension period (OL).

Study data collection will occur in-person at baseline and at weeks 4, 8, 12, and 16 and via phone 30-60- days after end-of-open label and 365- days after enrollment. Details of data collection are outlined in Tables 1 & 2 located on the last two pages of this proposal.

Study Population

Number of subjects

Sample size power calculations are based on using power = 0.8, with a two-tailed $\alpha=0.05$, and the a priori decision to detect a medium effect size ($d \geq .5$) with a primary parent-rated measure that is a combination of CASI-5 subscale scores. Given the three sites and two treatments; a 3:2 randomization ratio, active-to-placebo; and assuming two dropouts per arm, per site, based on a previous study (Rucklidge, 2017), ($n = 12$ total), sample needed to recruit = at least 135, with at least 123 retained. To account for the 3 sites and the 3:2 randomization, a number divisible by 15 is needed, so, $n = 45$ participants per site.

In terms of feasibility, we estimate being able to recruit the required number of participants over a period of 12-18 months, given proven success in recruitment for a vitamin D supplementation trial ([name]) and established success recruiting participants in a longitudinal study on ADHD ([name]).

Inclusion Criteria

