At the two US sites, the child participant will be paid \$10 per in-person assessment (n=5), in the form of a gift card, (see Table 1 for assessment schedule) for a total of \$50. Gift card payment will be made for each instance the child completes the questionnaires and measures associated with that assessment time point. If the child declines to answer any questions, questionnaires and measures despite reassurance or assistance including by parent and the study coordinator, or actively declines to participate at any visit, s/he will be discontinued from the study. Children will also be paid \$10 for each blood sample provided, and \$5 for each of the other biological samples they provide, for up to \$105 for each of the 3 time points. Except for blood, children will not be withdrawn from the study for not providing a biological sample (hair, saliva, stool, urine), but the samples collection will be prioritized as part of the study. Parent/guardians will be paid \$20 for traveling to the site for in-person assessments, for a total of 5 visits during the main, 16 weeks of the study (\$100), and additionally, \$10 for questionnaires completed online and over the phone at 2-month follow up, or \$20 for parents and \$10 for the child, if 2-month follow up occurs in person. One year after enrollment in the study, participant families will be contacted regarding their willingness to provide follow-up data including questionnaires and, potentially, biological samples. Parents and children will be paid for that in-person visit, or phone visit, according to the previously described schedule: \$10 for phone completion; \$20 to parent for in-person completion; \$10 to child for in-person completion; \$5 for each biological sample provided, except blood, \$10.

At the Canadian site, payment to participants is not expected or customary. As such, parents will be given \$25 gift vouchers for their participation in the qualitative part of the study (i.e. in-person interviews) and will be reimbursed for cost of travel, including parking and mileage per onsite visit. In Canada, blood and urine will not be collected due to storage limitations. Health Canada, the Canadian equivalent of the FDA, has not required collection of blood.

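### The Randomization section describes one scheme for all three sites in blocks of 5 with no stated site stratification, so the 3:2 ratio that the sample size section plans around is not guaranteed within site.

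*Combined protocol and SAP*

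**What the plan says.** The protocol's Randomization section states: "The randomization scheme will be generated for all three sites, as a whole, by the study statistician at OHSU using REDCap". The list uses one block size throughout, namely 5, with three active and two placebo assignments in each block. On distribution, the section says: "The randomization scheme will be emailed to the other two sites". A pharmacist or unblinded team member "at each site will prepare individual participant pill kits in advance, per the randomization scheme". On numbering, it adds: "These kits will be sequentially numbered and allocated to placebo or micronutrients based on the randomization list". Site is not named as a stratification factor. Nothing says whether the sites share one running sequence, receive separate runs of whole blocks, or each start at the top of the same list.

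Under Study Population, Number of subjects, the total is justified this way: "To account for the 3 sites and the 3:2 randomization, a number divisible by 15 is needed, so, $n = 45$ participants per site".

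The Data Analysis section compares arms by repeated-measures ANCOVA and names the baseline level as the covariate. Site is not mentioned there.

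**The concern.** An overall 3:2 ratio needs only a multiple of 5. The further factor of 3 gives equal sites of 45, and 45 is nine blocks of 5. That yields 27 active and 18 placebo at a site only if complete blocks are used at that site. A single list consumed by three sites as children arrive would split blocks across sites and lose this property. The two sections therefore do not fit together as written.

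Site balance matters here because the sites differ in conduct:
- The Setting and Recruitment text says "In Canada, blood and urine will not be collected due to storage limitations", and payment to families also differs in Canada.
- The CGI, named among the primary outcomes, draws on research assistant observation and PI overview.
- Dose increases are decided in consultation with the site PI.
- The Adherence section describes dispensing as varying by site.
- The DSMB is asked to look for safety differences by site.

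With site absent from the model, a chance association between site and arm would pass unadjusted into the estimate.

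**Working it through.** **Inputs.** From Number of subjects: 135 recruited, three sites, 45 per site, 3:2 allocation, d = 0.5, two-sided alpha 0.05. From Randomization: blocks of 5, 3 active to 2 placebo. Equal enrolment of 45 per site is the plan's own figure. Random arrival order across sites is an assumption.

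**The plan's figure.** 135 / 3 = 45 per site, and 45 / 5 = 9 blocks. Then 9 × 3 = 27 active and 9 × 2 = 18 placebo per site, or 81:54 overall. The multiple of 15 does what the section implies if blocks are complete within site. The 27:18 split is derived here; the protocol does not print it.

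**Case A: one running list, sites in random arrival order.** The active count at a given site is then hypergeometric: 45 drawn from 135, of which 81 are active.
- Mean = 45 × 81/135 = 27.
- Variance = 45 × 0.6 × 0.4 × (135 − 45)/(135 − 1) = 10.8 × 0.6716 = 7.25, so SD = 2.7.
- The 95% range is 22 to 32 active, hence 13 to 23 placebo.
- A given site is exactly 27:18 in about 15% of lists, and all three sites are in about 2.5%.
- At least one site is off by 3 or more in about 62%, and by 5 or more in about 21%.

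Simulation of 100,000 lists of 27 permuted blocks gives the same figures (SD 2.69, 62%, 21%, 2.5%).

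**Case B: whole blocks assigned to each site.** Every site is exactly 27:18.

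**Case C: each site works from the top of the same list.** Every site is again exactly 27:18, but a given position on the list then carries the same assignment at all three sites.

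**Cost in precision under Case A, site-adjusted analysis.** With a actives among a site's 45, its information is proportional to a(45 − a).
- Planned: 27 × 18 = 486.
- Expected: 486 − 7.25 = 478.75.
- Mean relative efficiency = 478.75/486 = 0.985.

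With 81:54 and SD 1, the standard error is √(1/81 + 1/54) = 0.1757. Power is Φ(0.5/0.1757 − 1.96) = 81.2%. With the standard error divided by √0.985, power is 80.6%. At the 5th percentile of efficiency (0.957) it is 79.5%. These powers use all 135 children and serve only as a scale; whether 123 retained is enough is a separate matter.

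**Size of an unadjusted imbalance under Case A.** If a site has a actives, its share of the active arm minus its share of the placebo arm is (a − 27)(1/81 + 1/54). The SD of that difference is 2.69 × 0.0309 = 0.083. Assume one site's mean outcome differs from the others by 0.3 SD (not a figure from the protocol). The resulting shift in the treatment estimate has SD 0.3 × 0.083 = 0.025, against a standard error of about 0.18.

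**The two US sites, for blood measures.** Planned actives are 54 of 90. Under Case A the range is 81 − 32 = 49 to 81 − 22 = 59. Mean pooled efficiency is (54 × 36 − 7.25)/(54 × 36) = 0.996.

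**The case against.** The phrase about all three sites as a whole can mean only that the list was produced centrally. Kits packed in advance at each site fit a divided list better than a shared one. If whole blocks were sent out, there is no imbalance. That reading stands as a possibility, so a reader who infers that 3:2 is broken within site goes further than the text allows. The aim of 27:18 per site is likewise a strong inference from the multiple of 15, not a stated goal. The text under Cross Site Coordination was not available to read and might describe how the list is shared.

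Two other strong readings also fail. One is that site imbalance would bias the result. Under valid randomization a chance imbalance leaves the estimator unbiased, and the figures above show that the likely shift and the loss of precision are small. The other is that one emergency unblinding would expose neighbouring assignments. In a 3:2 block of 5, on average 1.5 assignments are forced, but only for someone who knows every earlier one in the block. The protocol denies clinicians and participants that access. Learning one assignment moves another in the same block from 60% active to 50% or 75%, and an unblinded kit preparer already holds the list.

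Finally, blocks kept within a site are easier to predict locally than blocks spread over three sites, so stratification has a price. That is correct, and it is why the block size should vary if site strata are used.

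What remains is that the protocol gives no rule for dividing the list. One plausible reading loses the property for which the total was made a multiple of 15, and the analysis does not name site.

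**Conclusion.** The point holds in a limited form. As written, the 3:2 ratio is not guaranteed within site, although the sample size section plans for three sites and that ratio together. How large the departure is depends on how the list is divided. It is SD 2.7 actives per site under a shared running list with random arrival and 45 per site, and zero if whole blocks go to each site. The effect on power is about 0.6 percentage points on average. The main reasons to act are that the two sections should agree, that the ANCOVA leaves any chance imbalance between site and arm unadjusted, and that the remedy is nearly free. It does not threaten the trial's validity.

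**What to change.** In the Randomization section, state that randomization is stratified by site with permuted blocks within site. Each site has its own list of 45 (27:18), built from randomly mixed blocks of 5 and 10, because blocks kept within a site are locally more predictable. Send each list only to that site's unblinded kit preparer. In the Data Analysis section, add site as a covariate in the ANCOVA alongside baseline.

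The cost is new lists and a few sentences; N stays at 135. The downside is that a site stopping short of 45 may end inside a block and be off by a few children. The worst case is about 2.4 in a 6:4 block of 10: four placebo first, when 4 × 0.6 = 2.4 actives were expected. In a block of 5 it is 2 × 0.6 = 1.2.

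The documents do not say whether enrolment has begun; the protocol is headed 2017 and the IRB approval date is 23-Feb-2021. If it has, the list should not be regenerated. Document how it was divided between sites, report the arm counts by site, and add site to the model.
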